### 16.1.2. MISSING DATA METHODS FOR PRIMARY IMMUNOGENICITY VARIABLE(S)

Refer to Section 7.3.

### 16.1.3. PRIMARY ANALYSIS OF PRIMARY IMMUNOGENICITY VARIABLE

The following study hypotheses are ordered into 2 families that will be tested in sequential design with full alpha propagation. Family 1 will be tested first and family 2 will only be tested if the hypothesis in family one is successfully demonstrated.

First Co-Primary Immunogenicity Objective (Family 1):

The first co-primary immunogenicity objective is to demonstrate the immunological non-inferiority of the antibody response to MenABCWY vaccine, compared to MenACWY vaccine given to healthy participants, previously primed with MenACWY, as measured by percentage of participants with 4-fold rise (refer to Section 6.6) in hSBA titer against each of the *N. meningitidis* serogroups A, C, W, and Y, at 1 month after the **second** MenABCWY vaccination and 1 month after the MenACWY vaccination (single dose). This translates to the following hypotheses:

$$H_0: (p1\_MenABCWY_{(i)} - p1\_MenACWY_{(i)}) \leq -10\%$$

vs.

$$H_1: (p1\_MenABCWY_{(i)} - p1\_MenACWY_{(i)}) > -10\%$$

---

Document: C:\ProgramData\activePDF\Temp\DocConverter\API\input\99638a57dafd\$76D9DDEF7D8D4E7C  
B4DEE6C228977964.docx

Author: PPD

Version Number:

Final 5.0

**CONFIDENTIAL**

Version Date:

05SEP2022

Where  $p1\_MenABCWY_{(i)}$  denotes the percentages of participants with 4-fold rise (refer to Section 6.6) in hSBA titers for serogroups  $i=A, C, W,$  and  $Y,$  1 month after the **second** vaccination of MenABCWY group and  $p1\_MenACWY_{(i)}$  denotes the percentages of participants with 4-fold rise (refer to Section 6.6) in hSBA titers for serogroups  $i=A, C, W,$  and  $Y,$  1 month after the single vaccination of MenACWY group.

The primary immunogenicity analysis will be performed for the PPS. The primary immunological non-inferiority of the MenABCWY vaccine, compared to MenACWY vaccine, will be demonstrated if the lower limit (LL) of the 2-sided 95% CI for the group difference in percentages of participants achieving a 4-fold rise (refer to Section 6.6) in hSBA titers is above  $-10\%$ , for each serogroup.

For each of the serogroups A, C, W, Y the percentages of participants with 4-fold rise (refer to Section 6.6), and the corresponding exact 2-sided 95% CIs based on Clopper-Pearson method (Clopper and Pearson, 1934) will be calculated for each vaccine group at 1 month post **second** vaccination. The standardized asymptotic CIs between group differences in percentages will be derived using the method of Miettinen and Nurminen (Nurminen, 1985).

Second Co-Primary Immunogenicity Objective (Family 2):

The second co- primary immunogenicity objective is to demonstrate the immunological NI of the antibody response to MenABCWY vaccine, compared to MenACWY vaccine given to healthy participants, previously primed with MenACWY, as measured by percentage of participants with 4-fold rise (refer to Section 6.6) in hSBA titer against each of the *N. meningitidis* serogroups A, C, W, and Y, at 1 month after the **first** MenABCWY vaccination and 1 month after the MenACWY vaccination (single dose). This translates to the following hypotheses:

$$H_0: (p2\_MenABCWY_{(i)} - p2\_MenACWY_{(i)}) \leq -10\%$$

vs.

$$H_1: (p2\_MenABCWY_{(i)} - p2\_MenACWY_{(i)}) > -10\%$$

Where  $p2\_MenABCWY_{(i)}$  denotes the percentages of participants with 4-fold rise (refer to Section 6.6) in hSBA titers for serogroups  $i=A, C, W,$  and  $Y,$  1 month after the **first** vaccination of MenABCWY group

Document: C:\ProgramData\activePDF\Temp\DocConverter\API\input\99638a57dafd\$76D9DDEF7D8D4E7C B4DEE6C228977964.docx

Author: PPD

Version Number: Final 5.0

**CONFIDENTIAL** Version Date: 05SEP2022

and  $p2\_MenACWY_{(i)}$  denotes the percentages of participants with 4-fold rise (refer to Section 6.6) in hSBA titers for serogroups  $i=A, C, W,$  and  $Y,$  1 month after the single vaccination of MenACWY group.

The secondary immunological non-inferiority of the MenABCWY vaccine, compared to MenACWY vaccine, will be demonstrated if the lower limit (LL) of the 2-sided 95% CI for the group difference in percentages of participants achieving a 4-fold rise (refer to Section 6.6) in hSBA titers is above  $-10\%$ , for each serogroup

For each of the serogroups A, C, W, Y the percentages of participants with 4-fold rise (refer to Section 6.6), and the corresponding exact 2-sided 95% CIs based on Clopper-Pearson method (Clopper, 1934) will be calculated for each vaccine group, at 1 month after the **first** vaccination for the ABCWY group (Day 211, Month 7), and 1 month after the single dose of MenACWY vaccination for the ACWY group (Day 31, Month 1). The standardized asymptotic CIs between group differences in percentages will be derived using the method of Miettinen and Nurminen (Nurminen, 1985). The secondary immunological non-inferiority analysis will be performed for the PPS.

#### **16.1.4. SENSITIVITY ANALYSIS OF PRIMARY IMMUNOGENICITY VARIABLE(S)**

Each co-primary immunogenicity objective will be analysed as a sensitivity analysis using a logistic regression with margins calculated by Taylors approximation with the minimization factors as covariables.

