9.2 Sample Size Determination

The sample size calculation was based on data from the MenABCWY, V102_03E1 study after adjusting for the variabilities due to different settings of the study (e.g., differences in population, differences in antibody assays, and different strain for serogroup A) (Table 14).

Assuming that MenACWY group will induce a 4-fold rise in about 95% of the participants for each of the 4 serogroups; MenABCWY will induce a 4-fold rise in about 91% of the participants for A and W serogroups, and 93% of the participants for C and Y serogroups; and using a 1-sided score test (Miettinen, 1985), non-inferiority margin of -10% and actual margins as given in Table 14, an estimated number of evaluable participants ($n=542$) and individual powers of 96.00%, 99.95%, 96.00%, and 99.95% for each A, C, W, and Y serogroup test, will give a global power of 90% to demonstrate NI of MenABCWY vs MenACWY.

Family 1: Assuming that MenABCWY and MenACWY groups will induce a 4-fold rise in about 95% of the participants for each of the 4 serogroups (Table 14), and using a 1-sided score test (Miettinen, 1985), non-inferiority margin of -10% and actual margin of 0%, an estimated number of evaluable participants ($n = 225$) and individual powers of 99.87% for each A, C, W, and Y serogroup test, will give a global power of 99.48% to demonstrate non-inferiority of MenABCWY versus MenACWY.

Family 2: Assuming that MenACWY group will induce a 4-fold rise in about 95% of the participants for each of the 4 serogroups; MenABCWY will induce a 4-fold rise in about 91% of the participants for A and W serogroups, and 93% of the participants for C and Y serogroups; and, using a 1-sided score test (Miettinen, 1985), non-inferiority margin of -10% and actual margins as given in Table 14, an estimated evaluable participants ($n=542$) and individual powers of 96.00%, 99.95%, 96.00%, and 99.95% for each A, C, W, and Y serogroup test, will give a global power of 91% to demonstrate NI of MenABCWY versus MenACWY.

For the multiplicity adjustment, all hypotheses will be ranked into two families according to the following power of test:

Table 14 Power to Demonstrate Immunological Non-inferiority for Serogroups A, C, W, and Y of MenABCWY Compared to MenACWY (Primary)

Serogroup	4-fold rate	4-fold rate MenABCWY	NI margin	Actual margin	Power	N
	MenACWY					ABCWY/ ACWY
Family 1: NI, 2-sided score test (Miettinen and Nurminen, 1985)						
A	95%	95%	-10%	0%	99.87%	225

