9.4.4 Secondary Endpoints

9.4.4.1 Immune Response N. Meningitidis Serogroups A, C, W, and Y (Measured by hSBA)

Analysis set: The analysis will be based on the FAS.

Statistical method: For each of the 4 *N. meningitidis* serogroups A, C, W, and Y the percentages of participants with hSBA titers \geq LLOQ and the corresponding exact 2-sided 95% CIs based on Clopper-Pearson method ([Clopper and Pearson, 1934](#)) will be calculated for ABCWY and ACWY study groups. Refer to [Section 9.4.3.1](#) for the definition of 4-fold rise for the Men A, C, W, and Y evaluation.

Geometric mean titers and associated 2-sided 95% CIs will be computed for each group and for each strain at each visit. The titers at baseline (Day 1, Month 0), at 1 month after the first (Day 31, Month 1) and the last vaccination (Day 211, Month 7) for the ABCWY group, and at 1 month after the single MenACWY vaccination (Day 31, Month 1) in the ACWY group, will be logarithmically transformed (base10) to fulfill the normal distribution assumption.

Geometric mean titers and 95% CIs will be calculated by exponentiating (base 10) the least squares means and the lower and upper limits of the 95% CIs of the log-transformed titers (base10) obtained from a 2-way Analysis of covariance (ANCOVA) with factors for vaccine group and country. The ANCOVA will include baseline titers as covariate, and it will be performed to take into consideration the possible effect of these on the post-vaccination titers.

Geometric mean ratios (GMRs) (post-vaccination/baseline titer) and associated 2-sided 95% CIs will be computed for each group and for each strain at each visit. Geometric mean ratios will be calculated by exponentiating (base10) the least squares means and the lower and upper limits of the 95% CIs of the log-transformed titers (base10) obtained from a 2-way ANOVA with factors for vaccine group and country.

Additionally, GMTs and GMRs group ratios between the 2 intervention groups and their respective 95% CIs will be computed by exponentiating the difference of the least square means of the log-transformed titers and the lower and upper limits of the 95% CIs on the difference obtained from the ANCOVA/ANOVA model above.

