### 6.5. STATISTICAL TESTS

The default significance level will be (5%); confidence intervals will be 95% and all tests will be two-sided, unless otherwise specified in the description of the analyses.

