## **7.5. ACTIVE-CONTROL STUDIES INTENDED TO SHOW NON-INFERIORITY**

NI will be demonstrated if, the lower limit of 2-sided 95% confidence interval (CI) for the percent difference in 4-fold rise (refer to Section 6.6) in hSBA titers ( $p_{\text{MenABCWY}} - p_{\text{MenACWY}}$ ) is above -10%, for each N. meningitidis A, C, W, and Y serogroup. Additional details provided in Section 16 of this SAP.

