## 16.2.3. ANALYSIS OF SECONDARY IMMUNOGENICITY VARIABLES

### 16.2.3.1. Immune Response Analysis, Serogroups A, C, W and Y (measured by hSBA)

For each of the 4 *N. meningitidis* serogroups A, C, W, and Y the percentages of participants with hSBA titers  $\geq$ LLOQ and the corresponding exact 2-sided 95% CIs based on Clopper-Pearson method ([Clopper](#)) will be calculated at baseline (Day 1, Month 0), and at 1 month after the **first** (Day 31, Month 1) and the **last** vaccination (Day 211, Month 7) for the ABCWY group, and at baseline (Day 1, Month 0) and 1 month after the single MenACWY vaccination for the ACWY group (Day 31, Month 1).

The titers at baseline (Day 1, Month 0), at 1 month after the **first** (Day 31, Month 1) and the **last** vaccination (Day 211, Month 7) for the ABCWY group, and at 1 month after the single MenACWY vaccination (Day 31, Month 1) in the ACWY group, will be logarithmically transformed (base 10) to fulfill the normal distribution assumption.

GMTs and 95% CIs will be calculated by exponentiating (base 10) the least squares means and the lower and upper limits of the 95% CIs of the log-transformed titers (base 10) obtained from:

- an ANOVA with factors for vaccine group and country.
- an ANCOVA with baseline titers as a covariate, and factors for vaccine group and country.

GMRs (post vaccination/baseline titer) and associated 2-sided 95% CIs will be computed for each group and for each serogroup at each visit. GMRs will be calculated by exponentiating (base 10) the least squares means and the lower and upper limits of the 95% CIs of the log-transformed titers (base 10) obtained from an ANOVA with factors for vaccine group and country.

Additionally, GMTs and GMRs group ratios between the 2 vaccine groups and their respective 95% CIs will be computed by exponentiating the difference of the least square means of the log-transformed titers and the lower and upper limits of the 95% CIs on the difference obtained from the ANOVA model above.

---

Document: C:\ProgramData\activePDF\Temp\DocConverter\API\input\99638a57dafd\$76D9DDEF7D8D4E7C  
B4DEE6C228977964.docx

Author: PPD

Version Number:

Final 5.0

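### Baseline titer sets each participant's 4-fold threshold and is measured in everyone, yet the SAP leaves it out of the adjusted co-primary sensitivity model and out of the between-group GMT and GMR ratios

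*SAP*

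**What the plan says.** **Decision rule.** SAP 7.5 and 16.1.3 declare non-inferiority when the lower limit of the two-sided 95% Miettinen-Nurminen interval for the difference in 4-fold rise "is above -10%, for each N. meningitidis A, C, W, and Y serogroup". The interval is unadjusted.

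**Adjusted co-primary analysis.** SAP 16.1.4 adds a sensitivity analysis "using a logistic regression with margins calculated by Taylors approximation with the minimization factors as covariables". Protocol 6.3.3 and SAP 3.1 name country as the only minimization factor.

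**Role of baseline in the endpoint.** Protocol 9.4.1 and SAP 6.6 set the response threshold by baseline titer in three tiers. At or above the LLOQ, the participant must reach four times his or her own pre-vaccination titer.

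**Availability.** The footnotes to Protocol Table 11 (8.1.3) plan Day 1 testing for A, C, W and Y in all participants.

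**Titer models.** SAP 7.1 confines baseline titer to the ANCOVA models. For GMTs, SAP 16.2.3.1 lists two sources, the "log-transformed titers (base 10) obtained from: - an ANOVA with factors for vaccine group and country" and then an ANCOVA that adds baseline. GMRs come from an ANOVA on group and country. Protocol 9.4.4.1 says of the ANCOVA that "it will be performed to take into consideration the possible effect of these on the post-vaccination titers".

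**Between-group ratios.** Protocol 9.4.4.1 takes the GMT and GMR group ratios from the ANCOVA/ANOVA. SAP 16.2.3.1 takes both from the ANOVA alone. SAP 3.3 lists wider visit windows as the only change to the protocol's planned analyses.

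**The concern.** Inclusion criterion 4 requires a MenACWY dose at least 4 years before enrollment, so baseline titers can be expected to vary. A participant who starts above the LLOQ faces a higher bar for a 4-fold rise than one who starts below it. Baseline is therefore the natural covariate for response, and the protocol already treats it as one for GMTs.

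The sensitivity model adjusts for country and omits baseline. The subgroups in SAP 7.6 are sex, race, age and country, so they do not show it either. If the arms differ by chance in baseline, most likely in the smaller Day 211 sample used for Family 1, no planned analysis of 4-fold rise shows how much of the estimated difference that explains.

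For titers, the SAP fits the model that uses baseline but does not name its group contrast as a reported result. The reported ratios are then less precise than the data allow.

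**Working it through.** **1. The plan's own figures.** Inputs:
- SAP 6.5: "The default significance level will be (5%); confidence intervals will be 95% and all tests will be two-sided", so one-sided 0.025 for non-inferiority.
- Margin of -10 points (SAP 7.5).
- Protocol 9.2, control arm: "Assuming that MenACWY group will induce a 4-fold rise in about 95% of the participants for each of the 4 serogroups".
- Protocol 9.2, Family 2: "MenABCWY will induce a 4-fold rise in about 91% of the participants for A and W serogroups, and 93% of the participants" (the 93% applies to serogroups C and Y), 542 evaluable per group, "individual powers of 96.00%, 99.95%, 96.00%, and 99.95% for each A, C, W, and Y serogroup test".
- Protocol 9.2, Family 1: 95% in both arms, 225 evaluable, 99.87% per serogroup.

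Miettinen-Nurminen score test, normal approximation / exact enumeration:

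| Case | Stated | Recomputed |
|---|---|---|
| A, W (91% vs 95%, 542 per group) | 96.00% | 96.0% / 96.2% |
| C, Y (93% vs 95%, 542 per group) | 99.95% | 99.95% / 99.96% |
| Family 1 (95% vs 95%, 225 vs 542) | 99.87% | 99.87% / 99.79% |

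The stated powers are reproduced, and they are high without any adjustment.

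**2. Group ratio of titers.** Write Y for log10 post-vaccination titer, X for log10 baseline, G for group and C for country. The model Y - X = a + bG + cC + dX is the same as Y = a + bG + cC + (d + 1)X. In the same participants, b and its standard error are identical. A simulated check at rho = 0.5 gave a contrast of 0.0913 with SE 0.0532 from both. The baseline-adjusted GMR ratio is therefore the GMT ANCOVA ratio.

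With equal SDs before and after vaccination and correlation rho (assumed), the variances per participant are:
- ANOVA on change: 2(1 - rho)σ²
- ANOVA on post titer: σ²
- ANCOVA: (1 - rho²)σ²

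| rho | ANCOVA / change-score ANOVA = (1 + rho)/2 | ANCOVA / post-titer ANOVA = 1 - rho² |
|---|---|---|
| 0.2 | 0.60 | 0.96 |
| 0.4 | 0.70 | 0.84 |
| 0.6 | 0.80 | 0.64 |

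Against the change-score ANOVA, the interval on the log scale narrows by 1 - √0.60 = 23% at rho 0.2 and by 1 - √0.80 = 11% at rho 0.6.

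**3. 4-fold rise at the planned rate.** Let q be the share at or above the LLOQ at baseline, p₋ the response of the others, and overall response 0.95. Then p₊ = (0.95 - (1 - q)p₋)/q, and the share of outcome variance explained is R² = q(1 - q)(p₋ - p₊)²/(0.95 × 0.05). Adjustment multiplies the variance of the difference by about 1 - R². The SD of the chance difference in q between arms is √[q(1 - q)(1/225 + 1/542)]. The shift is that SD times (p₋ - p₊). The values of q and p₋ are assumed.

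| q | p₋ | p₊ | R² | SD of imbalance (points) | Shift (points) |
|---|---|---|---|---|---|
| 0.30 | 0.97 | 0.903 | 2.0% | 3.63 | 0.24 |
| 0.30 | 0.99 | 0.857 | 7.9% | 3.63 | 0.48 |
| 0.50 | 0.97 | 0.930 | 0.8% | 3.97 | 0.16 |
| 0.50 | 0.99 | 0.910 | 3.4% | 3.97 | 0.32 |

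**4. Check of the 1 - R² rule.** Simulated logistic models (91% vs 95%, 542 per group, 400 runs per scenario) compared country plus baseline with country alone. The variance ratio was about 1.00, 0.98, 0.90 to 0.92, 0.84 and 0.74 to 0.75 at control-arm R² of 0, 0.01, 0.06, 0.14 and 0.23. A baseline unrelated to response cost nothing material.

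**5. In terms of power.** For A and W at 91% vs 95%, the unadjusted 95% half-width is 1.96 × √[(0.91 × 0.09 + 0.95 × 0.05)/542] = 3.03 points. It falls to 2.95 at R² = 0.05 and 2.87 at R² = 0.10, which is equivalent to power of 96.8% and 97.5% instead of 96.0%. That gain would count only if the adjusted analysis made the decision, which is not proposed.

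**The case against.** The strongest reply has four parts.

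- **The logistic model decides nothing.** This stands. It is a sensitivity analysis whose stated purpose is to include the minimization factors, and it does so. Adding baseline leaves the deciding estimate and interval unchanged.
- **The Miettinen-Nurminen interval already allows for chance imbalance.** This stands as a statement about its coverage, and Protocol 8.1.3 selects the assay subsets at random. It does not remove the use of an adjusted estimate that shows what a particular imbalance did.
- **The protocol already provides the adjusted titer ratio.** This stands for the protocol: its ANCOVA/ANOVA wording covers it, and a new GMR model would repeat the GMT ANCOVA contrast. It does not hold for the SAP, which names the ANOVA alone as the source of both ratios.
- **More covariates may not be stable.** This stands in part. At 95% response, 225 participants yield about 11 non-responders (225 × 0.05), spread over approximately 4 countries (SAP 7.2). Three baseline tiers could give sparse cells. Titers below the LLOQ are set to LLOQ/2 (SAP 7.3), so a linear log10 term is only approximate. The fix needs a simpler fallback.

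A reader might also infer that the change-score ANOVA is biased by regression to the mean. In a randomized comparison its group contrast is unbiased; it is only less precise.

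**Conclusion.** The point holds as a matter of precision and completeness. The single adjusted check on each co-primary result omits the variable that sets the response threshold. The SAP's group ratios also drop a baseline adjustment that the protocol allows, and SAP 3.3 does not declare this as a change.

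The size is moderate for titers. The variance of the log GMR ratio would be multiplied by 0.60 to 0.80 for rho between 0.2 and 0.6, assuming equal SDs. It is small for 4-fold rise. The variance reduction is about 1 to 8%, and a one-SD imbalance shifts the difference by about 0.2 to 0.5 points against a 10-point margin. That rests on 95% response in both arms, 30 to 50% baseline-positive and 97 to 99% response among the rest. Neither document gives any of these associations.

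Three stronger readings are tempting and not supported:
- **The non-inferiority decision is compromised.** It rests on the unadjusted interval, which is valid here.
- **The trial is underpowered without baseline.** The stated powers of 96.00% or more are reproduced with no adjustment.
- **The gain for 4-fold rise is much larger.** That needs a steep drop in response among baseline-positives. With response of 65% in them, overall response would be 0.5 × 0.97 + 0.5 × 0.65 = 81% to 0.7 × 0.99 + 0.3 × 0.65 = 89%, which contradicts the planned 95%.

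**What to change.** 1. **SAP 16.2.3.1.** Take the between-group ratio and its 95% CI from the ANCOVA with log10 baseline titer of the relevant serogroup, vaccine group and country. State that the adjusted GMT ratio and the adjusted GMR ratio are the same contrast, and report it once. Protocol 9.4.4.1 needs no new model.
2. **SAP 16.1.4.** Add log10 baseline titer of the relevant serogroup beside country. Prespecify an indicator for baseline below versus at or above the LLOQ as the replacement if cells are sparse. Report the standardized risk difference with 95% CI for both families.
3. **SAP 7.1.** Extend the list of models that use baseline titer to match.

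Keep the unadjusted Miettinen-Nurminen interval as the decision rule.

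The cost is one covariate in one model and a changed source for one reported contrast, with no new samples or assays. The edit should be made before group-level immunogenicity results are seen, including those of the interim analysis that SAP 4.2 allows.

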#### **16.1.5. SUBGROUP ANALYSIS OF PRIMARY IMMUNOGENICITY VARIABLE(S)**

The primary immunogenicity variables will be analysed for subgroups listed in Section 7.6

## **16.2. SECONDARY IMMUNOGENICITY**

The secondary immunogenicity analyses will be performed for the FAS.

### **16.2.1. SECONDARY IMMUNOGENICITY VARIABLES & DERIVATIONS**

#### **16.2.1.1. Immune Response, Serogroups A, C, W and Y (measured by hSBA)**

---

Document: C:\ProgramData\activePDF\Temp\DocConverter\API\input\99638a57dafd\$76D9DDEF7D8D4E7C  
B4DEE6C228977964.docx

Author: **PPD**

Version Number:

Final 5.0

**CONFIDENTIAL**

Version Date:

05SEP2022

The immune response to MenABCWY (0,6-month schedule) and MenACWY (single dose) vaccines against *N. meningitidis* serogroups A, C, W, and Y, at pre-vaccination (Day 1, Month 0) and 1 month after the **first and last** MenABCWY vaccinations and 1 month after the single MenACWY vaccination will be demonstrated using:

- Logarithmically transformed (base 10) hSBA titers and percentages of participants with hSBA titers  $\geq$ LLOQ:
  - at baseline (Day 1, Month 0) and at 1 month after the first (Day 31, Month 1) and the last vaccination (Day 211, Month 7) for the ABCWY group, and
  - at baseline (Day 1, Month 0) and 1 month after the single MenACWY vaccination for the ACWY group (Day 31, Month 1).

